2.4 Treatments (study treatment, rescue medication, concomitant therapies)

2.4.1 Study treatment exposure

Extent of exposure to study treatment is calculated as the number of IVT injections received.

The following summaries will be presented:

- 1. Overall number of injections (n, q1, median, q3, min and max) will presented.
- 2. Number of injection (n, q1, median, q3, min and max) before or at Week 8 and greater than Week 8.
- 3. Number of patients with injection (1 injection, 2 injections up to the maximum number of injections) from Baseline to the end of the treatment period will be presented.
- 4. Treatment exposure by visit: The number and percentage of patients who received injections, missed a treatment and missed visits will be presented by visit.
- 5. Summary statistics (n, mean, std, median, min and max) for overall duration will be provided.

The number and percentage of patients for changes in brolucizumab 6 mg treatment patterns over time (i.e. interruptions or permanent discontinuations) along with reasons, will be summarized. Discontinuations and primary reasons for treatment and/or study discontinuation will also be described.

Exposure data will be summarized for the Safety Set and FAS. The exposure data will be listed for the FAS.

2.4.2 Prior, concomitant and post therapies

Each medication has the start and end dates recorded on the eCRF. Prior medications are defined as those medications which were taken and stopped prior to first dose of study treatment. Concomitant medications are defined as any medication given at least once between the day of first dose of study treatment and the last day of study visit, including those which were started pre-baseline and continued into the treatment period. The below summary tables will be reported:

- Prior medication
- Concomitant medications which started prior to first dose of study treatment
- Concomitant medications which started on/after first of study treatment

All prior and concomitant medications will be coded using the most recent version of the WHO drug dictionary. All concomitant medications (general and ocular) will be listed and summarized in alphabetic order according to anatomical therapeutic chemical (ATC) classification system and PT. Tables will also show the overall number and percentage of patients receiving at least one treatment of a particular ATC.

For prior and concomitant ocular medications, as well as ocular procedures performed during the study, separate tabular summaries will be prepared for the any eye, study eye and the fellow eye. A listing of all prior and concomitant medications and concomitant procedures will be provided.

For handling of missing or incomplete start and end dates, see Appendix 5.1.3 of this document. All summaries will be performed on the Safety Set.

2.4.3 Prior and concomitant surgery and procedures

All prior and concomitant surgery and procedures will be summarized and listed by category (general, ocular) and eye (any eye, study eye and fellow eye).

For handling of missing or incomplete start and end dates, see Appendix 5.1.3 of this document. All summaries will be performed on the Safety Set.

2.5 Analysis of the primary objective

2.5.1 Primary endpoint

OCT-A will be used in this study to assess the morphological response of patients to brolucizumab. In terms of percentage change in CNV lesion area (at the biggest surface) (mm²).

The primary endpoint is the percentage change in CNV lesion area measured by OCT-A from Baseline to Week 12 in the study eye. The percentage change from Baseline at Week 12 in the lesion area will be derived as follows:

([Lesion area at Week 12 – Lesion area at Baseline]*100)/ Lesion area at Baseline

Descriptive statistics (n, mean, std, median, min and max) for the primary endpoint (actual value, change from Baseline, percentage change from Baseline) will be presented based on observed data using the FAS. Furthermore, a 2-sided 95% CI using Student's t-distribution will also be provided. In case of significant outliers or deviations from normality assumptions then IQR will be presented.

The last observation carried forward (LOCF) method will be used as sensitivity analysis to impute missing record for CNV lesion area at post baseline. If there is significant amount of missing record then another table with LOCF records should be created.

The above analysis will be done only on the study eye. The analysis will be performed on FAS. The analysis will be performed on the PPS, if there is more than a 10% difference in patients, between the FAS and PPS.

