Data analysis	
Primary analysis data set
 
The primary data set for efficacy evaluation is the full analysis set (FAS). The FAS includes all patients to whom study treatment has been assigned and who received at least one IVT injection of study treatment. Supportive and sensitivity analyses will be performed which may include using the Per Protocol Set (PPS) and alternative methods of handling missing values including a mixed model repeated measures (MMRM).
 
Primary endpoint
 
The primary endpoint is the percentage change from baseline in CNV lesion area measured by OCT-A at Week 12.
 
Primary statistical method
 
Descriptive statistics for the primary endpoint (actual value, change from baseline, percentage change from baseline) will be presented based on observed data using the FAS. Furthermore a 2-sided 95% confidence interval (CI) using Student's t-distribution will also be provided.
 
The interim database lock for the primary analyses will be conducted when the last patient included completed Week 12 visit. Subjects will remain in the study and will continue to receive treatment through the planned study duration of 48 weeks, to allow for further evaluation of efficacy and safety.
 
Sample size justification
 
A sample size of 180 to 400 patients produces a 2-sided 95% CI with a distance from the mean difference in percentage change in CNV lesion area

	measured by OCT-A from baseline to Week 12 to the limits ranging from 5.1 to 3.4 when the estimated standard deviation is 35. Therefore, to have a precision of 5.0%, a sample size of 189 patients will be needed. To take into account a dropout rate and uninterpretable images of 10%, a total of 210 patients will be included.
Ethical and regulatory obligations	The study will be performed in accordance with 

• The European Directive 2001/20/EC.

• The European General Data Protection Regulation.

• The ICH Harmonized Tripartite Guidelines for GCP.

• The ethical principles laid down in the Declaration of Helsinki.

Key words	Neovascular age-related macular degeneration, anti-VEGF, choroidal neovascularization, OCT-A

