### **12.4.3 Handling of missing values/censoring/discontinuations**

For patients who:

- Discontinue study treatment but continue in the study, the efficacy data will be censored at the time the patient stopped study treatment in the study eye.
- Interrupt treatment, the efficacy data will be censored at the time the study treatment was first interrupted.

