#### 12.4.4 Estimand and Sensitivity analyses

In case of significant outliers or deviations from normality assumptions, a non-parametric analysis may be performed.

In order to assess the robustness of the primary endpoint, estimand and sensitivity analyses are planned. These may include, but are not limited to:

- Consistent results from analyses based on the FAS and the PPS increases confidence in the trial results. Difference between FAS and PPS in incidence of intercurrent of event like COVID-19 regardless of whether patients discontinue assigned treatment. Performing comparison on the observed data between FAS vs PPS with the same handling rules for censoring as outlined in [Section 12.4.3](#). for the efficacy endpoints.
- Repeating the primary analysis using the PPS.

**Sensitivity estimand in exposed and non-exposed to the urgent safety measures:** As a sensitivity analysis for the change in CNV lesion area measured by OCT-A at Week 12, the change in CNV lesion area measured by OCT-A at Week 12 will be compared before and after the urgent safety measures were introduced. The analyses will be performed in FAS and PPS.

Further details about the analyses will be given in the SAP. Any major discrepancies in the results across analyses will be investigated as needed.

Age, Baseline lesion type, and time since nAMD diagnosis subgroup analyses will also be performed on the primary endpoint.

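### SAP 2.5.1 relies on LOCF alone, with an undefined trigger, to check the primary endpoint against missing data; a mixed model on readings already collected should be the main check

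*SAP*

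**What the plan says.** SAP 2.5.1 defines the endpoint: "The primary endpoint is the percentage change in CNV lesion area measured by OCT-A from Baseline to Week 12 in the study eye". Its descriptive statistics and t-based 95% CI "will be presented based on observed data using the FAS", so patients without a Week 12 reading drop out of the estimate.

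The only missing-data method in the SAP follows: "The last observation carried forward (LOCF) method will be used as sensitivity analysis to impute missing record for CNV lesion area at post baseline". The next sentence makes the output conditional: "If there is significant amount of missing record then another table with LOCF records should be created". No threshold is given. Nor does the section say what happens when Baseline is the only reading.

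The protocol summary is wider but not binding. Its list is worded permissively: "Supportive and sensitivity analyses will be performed which may include using the Per Protocol Set (PPS"). MMRM enters only as one further possibility under that same wording: "alternative methods of handling missing values including a mixed model repeated measures (MMRM"). Protocol 12.4.4 opens its own list with "These may include, but are not limited to" and names neither MMRM nor LOCF. Its items (the PPS repeat, and the comparison before and after the urgent safety measures) do not address missing values.

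Protocol 12.4.3 creates some of the missing data: for patients who stop treatment but stay in the study, "the efficacy data will be censored at the time the patient stopped study treatment in the study eye". Interruption is handled in the same way.

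**The concern.** Injections are given on Day 1, Week 4 and Week 8 (Protocol 3), and efficacy assessments come before the injection at each visit (Protocol 8). The Week 4 image therefore reflects one loading dose and the Week 8 image two. LOCF would put one of these in place of a Week 12 value that should reflect three, and would treat it as a real observation when the CI is computed.

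The observed-data estimate is itself biased if poorer responders are more likely to lack a Week 12 reading. That is possible here, because data are censored at discontinuation and discontinuation can follow lack of efficacy (Protocol 6.2.3). A sensitivity analysis should show whether this matters. LOCF is not valid in general when data are missing at random, so a gap between the two tables cannot be interpreted. In a single-arm study whose main result is one mean and its interval, this check carries weight. Lesion area is read centrally at Weeks 4, 8 and 12 (Protocol 8.3.1), so a better check needs no new data.

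**Working it through.** **1. The plan's own figure.** Inputs from Protocol 12.8.1 are SD 35, two-sided 95% CI, half-width 5.0 and 10% loss.
- Normal formula: n = (1.96 × 35 / 5)² = 188.2, rounded up to 189. Then 189 / 0.90 = 210. Both figures reproduce.
- With the t-distribution, the half-width at n = 189 is 1.973 × 35 / √189 = 5.02, which prints as 5.0.

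**2. LOCF under random dropout.** If a share m of patients is imputed and the carried value differs from the Week 12 value by d points on average, the LOCF mean shifts by m × d. At m = 0.10 (21 of 210):
- d = 5, 10, 20 or 30 gives a shift of 0.5, 1.0, 2.0 or 3.0 points toward a smaller reduction.
- d = 0 gives no shift.
- d = −10 gives 1.0 point the other way.
- A shift equal to the planned half-width needs d = 5.0 / 0.10 = 50 points.

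The documents give no Week 4 or Week 8 lesion areas, so the trajectories below are assumptions. Suppose half of the missing patients carry Week 4 and half carry Week 8:

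| Assumed mean % change, Weeks 4/8/12 | Average gap d | Shift at 10% |
|---|---|---|
| −20/−32/−40 | (20 + 8)/2 = 14 | +1.4 |
| −30/−40/−45 | (15 + 5)/2 = 10 | +1.0 |
| −25/−45/−65 | (40 + 20)/2 = 30 | +3.0 |
| Plateau at −30 | 0 | 0 |
| Rebound −30/−35/−28 | (−2 − 7)/2 = −4.5 | −0.45 |

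A positive shift means that the reduction is understated. If Week 12 alone is missing, only Week 8 is carried, and the first three rows become 0.8, 0.5 and 2.0.

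**3. LOCF when poorer responders leave.** This was simulated with n = 210, SD 35, assumed correlation 0.6 between visits, about 10% missing at Week 12, and log-odds of dropout rising by 1 per SD of the last observed value (400 trials per row). The model column is multivariate-normal maximum likelihood on the three visits, which is what an MMRM with visit means and unstructured covariance fits. Bias is in percentage points:

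| Weeks 4/8/12 | LOCF | Observed data | Model |
|---|---|---|---|
| −20/−32/−40 | +2.6 | −2.2 | −0.1 |
| −30/−40/−45 | +2.1 | −2.2 | −0.2 |
| −25/−45/−65 | +4.1 | −2.0 | −0.1 |
| Plateau −30 | +1.2 | −2.0 | 0.0 |
| Rebound −30/−35/−28 | +0.7 | −2.2 | −0.2 |

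Other runs of the falling trajectories gave LOCF bias up to +4.8, hence the range of about 2 to 5 points. In the three falling rows above, the LOCF and observed-data tables differ by 4.8, 4.3 and 6.1 points, about the size of the planned half-width, and neither is right. Flooring values at −100 left the model within about 0.2.

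**4. Precision.** Counting imputed values as observed narrows the half-width from 5.02 (n = 189) to 1.971 × 35 / √210 = 4.76 at the same SD.

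**5. If Baseline were carried.** The SAP wording leaves this open. Carrying Baseline enters a 0% change. With the reductions cited in Protocol 1.1, 10% missing shifts the mean by 0.10 × 11.3 = 1.1, 0.10 × 24 = 2.4 or 0.10 × 65 = 6.5 points.

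**The case against.** **No commitment is broken.** A reader might infer that the SAP replaced an analysis the protocol had promised. The documents do not support that. MMRM is an optional example in the protocol summary, it is absent from Protocol 12.4.4, and Protocol 12 leaves further detail to the SAP. SAP section 4, on changes to protocol-specified analyses, shows no text in the copy available, so nothing follows from its silence. This stands in full.

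**The direction is not fixed.** A reader might also infer that LOCF must understate the reduction. That needs either continued shrinkage to Week 12 or selective dropout. Protocol 4.1 chose Week 12 because the pivotal trials showed peak efficacy then, but Protocol 1.1 says those trials did not use OCT-A. With random dropout, a plateau gives no bias and a rebound reverses the sign. This stands too.

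**The simulation favours the model.** The data are generated as normal and missing at random, which is what the model assumes, and the dropout strength has no source in the documents. The −65 scenario with SD 35 puts about 16% of values below −100, which is impossible for a percentage change. Flooring at −100 answers the last point. The others mean that the sizes are illustrative, and that the model's advantage depends on missing at random.

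**The estimand.** Protocol 12.4.1 describes the effect at Week 12 while on study treatment, and SAP 2.1.1 uses efficacy data at the time treatment stopped. A last on-treatment value can be read as consistent with that wording, whereas an MMRM targets the Week 12 value had treatment continued. This is the strongest point, and it is why LOCF need not be deleted.

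**Limited reach.** Part of the 10% is uninterpretable Baseline images, which neither method can rescue. A patient who stops after the Week 8 injection has an early-discontinuation OCT-A four weeks later (Protocol Table 8-1), near Week 12, although whether it counts depends on how the censoring date is set. In the selective-dropout runs the two tables bracket the truth, but under random dropout the observed-data mean is right and LOCF alone is off. The reader of the tables cannot tell which case applies.

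**Conclusion.** The point holds as a weakness of the sensitivity analysis. LOCF is the SAP's only missing-data method for the primary endpoint, its table has no defined trigger, and it fills Week 12 with images taken after one or two of three loading doses. At the planned 10% missing, its mean would be off by about 1 to 3 points under falling trajectories with random dropout, and about 2 to 5 points if poorer responders leave. Under random dropout with a plateau or rebound, the error is nil or slightly the other way. These sizes rest on assumed trajectories, SD 35 and, for selective dropout, an assumed correlation of 0.6 and an assumed dropout strength.

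The primary observed-data estimate and CI do not change, and neither do the sample sizes of 189 and 210. It would go too far to say that the primary result is distorted by LOCF. What is lost is an interpretable robustness check. The change should be made, but it is not critical.

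**What to change.** In SAP 2.5.1:
- Always run an MMRM of percentage change in CNV lesion area at Weeks 4, 8 and 12, with visit as a factor, baseline lesion area as a covariate and unstructured covariance, on the on-treatment data of the FAS. Drop the undefined trigger.
- Report the Week 12 mean with its 95% CI as the main missing-data sensitivity analysis.
- State that it targets the Week 12 value had treatment continued, assuming missing at random.
- Keep LOCF, if wanted, as a supplementary last-on-treatment summary, and state that Baseline values are not carried forward.

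The cost is a SAP wording change and one more model-based table to explain. No new data are needed.

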2.5.2 Supportive analyses

Subgroups analyses according to patient characteristics, like sex (male, female), age class (≤ 64 , > 65 - 75, 75 - 85, ≥ 85), Baseline lesion type (type 1, type 2, type 3) and time since nAMD diagnosis (< 1 month, 1-3 months, and > 3 months).

2.6 Analysis of secondary efficacy objectives

2.6.1 Secondary endpoints

2.6.1.1 Oct-A long-term effects

The first secondary endpoint is the percentage change in CNV lesion area (mm²) measured by OCT-A for nAMD patients from Baseline to Week 48. Descriptive statistics (n, mean, std, median, min and max) for the change in CNV lesion (actual value, change from Baseline, percentage change from Baseline) will be presented based on observed data by visit. Furthermore, a 2-sided 95% CI using Student's t-distribution will be provided.

The number and percentage of lesion type (predominantly classic, minimally classic and occult) will be presented by visit.

The above analysis will be done only on the study eye. The analysis will be performed on the FAS.

